9.8.3 REPORTING OF NON-SERIOUS ADVERSE EVENTS

The collection of non-serious AE information should begin following the subject's written consent to participate in the study. All non-serious adverse events (not only those deemed to be treatment-related) should be collected continuously during the treatment period and for a minimum of 100 days following the last dose of study treatment.

Non-serious AEs should be followed to resolution or stabilization, or reported as SAEs if they become serious. Follow-up is also required for non-serious AEs that cause interruption or discontinuation of study drug and for those present at the end of study treatment as appropriate.

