8. Patient must provide adequate tumor tissue (core or surgical/incisional/excisional biopsy) prior to starting study for analysis for gene expression of LAG3 and CTLA4 per OmniSeq Immune Report Card. FNA is not adequate. Archival tissue can only be used if it was obtained in the recurrent/metastatic setting and no subsequent treatment was received after biopsy. If this is not available a new biopsy is needed. If a patient undergoes a second biopsy on trial for potential retreatment a new biopsy of adequate tumor tissue (as defined above) will need to be obtained.
9. Tumor imaging is required at baseline and then every 8 weeks (± 7 days) during study treatment. Unless there is a dose delay, imaging should be done within 7 days prior to odd cycles. If a patient completes 24 cycles without progression repeat imaging will be done every 3 months (± 7 days) from last receipt of study therapy as per section 7.7. Tumor imaging should be at minimum with a CT neck with IV contrast, CT chest with IV contrast, and CT abdomen/pelvis with IV contrast. If MRI is determined to be a better modality to follow the patients malignancy an MRI can be used. If a patient has an allergy to CT contrast dye that precludes usage than MRI can be used for disease in the head and neck and CT non-contrast can be used for the chest, abdomen and pelvis if the investigator has determined that tumor measurements can be made without the usage of CT IV contrast.

7.2 STUDY CALENDAR FOR PATIENTS TREATED WITH NIVOLUMAB AND RELATLIMAB (CYCLE = 28 DAY)

Assessments	C1D1	C1D14 (±3d)	C2D1 (± 3d)	C2D14 (±3d)	C3D1 and D1 of all subsequent cycles (± 3d)	Safety Follow up ^B	Survival Follow up ^C
Administer Nivolumab ^A	X		X		X		
Administer Relatlimab ^A	X		X		X		
Medical History	X		X		X	X	X
Medication History	X		X		X	X	
Physical examination	X	X	X	X	X	X	
Vital Signs and Weight ¹	X	X	X	X	X	X	
ECOG PS	X	X	X	X	X	X	
12 Lead EKG ²	X	X	X	X	X		
Review adverse events	X	X	X	X	X	X	
Pregnancy Test ³	X						
CBC w/ differential ^{4,5}	X	X	X	X	X	X	
Comprehensive Metabolic Panels ⁵	X	X	X	X	X	X	
TSH, FT4, T3 ⁶					X		
Troponin ^{2,7}	X	X	X	X	X		
Tumor Tissue ⁸							
Biomarker Studies/ Microbiome ⁹	X				X (Cycle 3 only)		
Tumor Imaging ¹⁰					X		

1. Vital signs to include temperature, pulse, respiratory rate, blood pressure. Height will be recorded at screening visit only.

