10. Tumor imaging is required at baseline and then every 8 weeks (+/- 7 days) during study treatment. Unless there is a dose delay, imaging should be done within 7 days prior to odd cycles. If a patient completes 24 cycles without progression repeat imaging will be done every 3 months (+/- 7 days) from last receipt of study therapy as per section 7.7. Tumor imaging should be at minimum with a CT neck with IV contrast, CT chest with IV contrast, and CT abdomen/pelvis with IV contrast. If MRI is determined to be a better modality to follow the patients malignancy an MRI can be used. If a patient has an allergy to CT contrast dye that precludes usage than MRI can be used for disease in the head and neck and CT non-contrast can be used for the chest, abdomen and pelvis if the investigator has determined that tumor measurements can be made without the usage of CT IV contrast.

A See section 7.4 for details of treatment with Relatlimab plus Nivolumab

B For patients with progressive disease who don't qualify for a second treatment on study per section 7.6, or who are withdrawn from the study for any reason including toxicity, safety follow up will occur for patients that discontinue trial treatment for any reason 30 days (+/- 7 days) after the last dosage of study drug combination

C For patients with progressive disease who don't qualify for a second treatment on study per section 7.6, or who are withdrawn from the study for any reason including toxicity, survival follow up will occur starting 3 months after the last dosage of study drug. A call will be placed to the patient for survival status and if alive whether subsequent anti-neoplastic therapy was received. Patient will receive calls every 3 months for the first year and then every 6 months for the second year, then yearly thereafter.

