7. Blood will be drawn for correlative studies. Instructions on tubes needed for biomarkers study blood draws are in section 14.0. They will be drawn prior to first dosage of study drug combination C1D1, and C3D1 prior to infusion, and at next study visit after progression is confirmed. Microbiome studies as per section 14.0 will also be obtained at these same timepoints.
8. Tumor imaging is required at baseline and then every 8 weeks (+/- 7 days) during study treatment. Unless there is a dose delay, imaging should be done within 7 days prior to odd cycles. If a patient completes 24 cycles without progression repeat imaging will be done every 3 months (+/- 7 days) from last receipt of study therapy as per section 7.7. Tumor imaging should be at minimum with a CT neck with IV contrast, CT chest with IV contrast, and CT abdomen/pelvis with IV contrast. If MRI is determined to be a better modality to follow the patients malignancy an MRI can be used. If a patient has an allergy to CT contrast dye that precludes usage than MRI can be used for disease in the head and neck and CT non-contrast can be used for the chest, abdomen and pelvis if the investigator has determined that tumor measurements can be made without the usage of CT IV contrast.

A See section 7.5 for details of treatment with Ipilimumab plus Nivolumab

B For patients with progressive disease who don't qualify for a second treatment on study per section 7.6 or who are withdrawn from the study for any reason including toxicity a safety follow up will occur 30 days (+/- 7 days) after the last dosage of study drug combination

C For patients with progressive disease who don't qualify for a second treatment on study per section 7.6, or who are withdrawn from the study for any reason including toxicity, survival follow up will occur starting 3 months after the last dosage of study drug. A call will be placed to the patient for survival status and if alive whether subsequent anti-neoplastic therapy was received. Patient will receive calls every 3 months for the first year and then every 6 months for the second year, then yearly thereafter.

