- Patient will not need to undergo repeat testing for HIV and Hepatitis B and C
- Patients will undergo serum collection for correlative studies before initiation of second treatment.

7.7 FOLLOW UP SCHEDULE FOR PATIENTS THAT COMPLETE 24 CYCLES OF THERAPY WITHOUT PROGRESSION OF DISEASE

If a patient completes all 24 cycles of therapy without progression the patient will be seen as per safety follow up visit at 30 days (+/- 7 days) and then every 3 months (+/- 7 days) from the last receipt of study therapy. Patient will undergo repeat imaging every 3 months and may be eligible for retreatment as per section 7.4 if the patient progresses.

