9.8.2 REPORTING OF SERIOUS ADVERSE EVENTS

All events meeting the definition of a serious adverse event (per section 9.1-9.4) including pregnancy should be reported according to the departmental SAE checklist and SAE form. Serious adverse events are collected from the date of the subject's first dose of treatment until 100 days after the final dose. The initial SAE form should be sent to the following within 24 hours/1 business days of the Sponsor-Investigator becoming aware:

1. [name]
2. [contact]
3. Local Institutional Review Board when reporting requirements are met.
4. Email to [contact] or by [contact]

SAEs, whether related or not related to study drug, and pregnancies must be reported to BMS within 24 hours \ 1 Business Day of becoming aware of the event. SAEs must be recorded on the internal departmental SAE form.

If only limited information is initially available, follow-up reports are required. (Note: Follow-up SAE reports should include the same investigator term(s) initially reported.)

If an ongoing SAE changes in its intensity or relationship to study drug or if new information becomes available, a follow-up SAE report should be sent within 24 hours \ 1 Business Day to BMS using the same procedure used for transmitting the initial SAE report.

All SAEs should be followed to resolution or stabilization.

In addition to completing appropriate patient demographic and suspect medication information, the report should include as applicable the following information that is available at the time of report within the Sections B and C of the departmental SAE form:

- CTCAE term(s) and grade(s)
- current status of study drug
- all interventions to address the AE (testing and result, treatment and response)
- hospitalization and/or discharge dates
- event relationship to study drug

Follow-up reports:

All SAEs should be followed to resolution or stabilization. Additional information may be added to a previously submitted report by adding to the original departmental SAE form and submitting it as follow-up or creating supplemental summary information and submitting it as follow-up with the original departmental SAE form. All follow-up forms must include the date the form is revised.

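### Adverse events are to be collected to day 100 after the last dose, but for patients who stop early the last scheduled adverse event review is at day 30

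*Combined protocol and SAP*

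**What the plan says.** **Collection window.** Section 9.8.3 asks for all non-serious adverse events, related or not, throughout treatment and "for a minimum of 100 days following the last dose of study treatment". Section 9.8.2 has serious events collected from the first dose "until 100 days after the final dose".

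**Calendars.** In sections 7.2 (relatlimab) and 7.3 (ipilimumab), the row "Review adverse events" is ticked at the on-treatment visits and at safety follow-up. It is blank under survival follow-up. The medical history row is ticked there; the medication history row is not.

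**Timing and content of the contacts.** Footnote B in 7.2 puts safety follow-up at "30 days (+/- 7 days) after the last dosage of study drug combination". Footnote B in 7.3 agrees: "a safety follow up will occur 30 days (+/- 7 days) after the last dosage of study drug combination". Footnote C then says that "survival follow up will occur starting 3 months after the last dosage of study drug" and gives the content: "A call will be placed to the patient for survival status and if alive whether subsequent anti-neoplastic therapy was received". Footnote C covers patients who progress and do not qualify for second treatment, and patients withdrawn for any reason, including toxicity.

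**Patients who complete 24 cycles without progression.** Section 7.7 has them seen at 30 days "and then every 3 months (+/- 7 days) from the last receipt of study therapy". Section 9.7 provides for adverse event questions at every study visit.

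**Use of the data.** Section 15.2.2 analyses safety as whether each participant had at least one serious event with at least a possible link to treatment. It also tabulates adverse events by type, grade and relatedness.

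**The concern.** The reporting section and the visit schedule do not match. A site that follows the calendars exactly has no scheduled point after about day 30 at which a patient who stopped early is asked about new adverse events, although the reporting section keeps the window open to day 100.

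The protocol's own background shows that serious toxicity can appear this late. Section 2.4.5 describes two phase 3 ipilimumab trials in prostate cancer. One had two toxicity deaths from events with onset more than 70 days after the last dose. The other had one toxicity death more than 70 days after the last dose and a further subject with fatal related events beyond that point. Those trials used 10 mg/kg, well above the dose here, so they show that late events occur and say nothing about their rate in this trial.

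Safety is a secondary objective. A related serious event that nobody asks about can only lower the observed rate. The patients with the thinnest follow-up include those who stopped because of toxicity.

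**Working it through.** The plan states no figure for this gap, so there is none to reproduce. The check sets the collection window against the scheduled contacts, in days after the last dose.

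**Inputs**
- Window closes at day 100 (9.8.2, 9.8.3).
- Last ticked adverse event review: day 30 +/- 7 (7.2 and 7.3, footnote B).
- First survival call: 3 months, about day 90 to 92 (footnote C, which gives no visit window).
- Completers' first 3-month visit: 3 months +/- 7 days (7.7).
- Sample size: 40 (15.4).

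**Step 1. Patients who stop early: days with no scheduled review**
- Last review: 30 − 7 = day 23 to 30 + 7 = day 37.
- Nominal gap: 100 − 30 = 70 days.
- Range: 100 − 37 = 63 to 100 − 23 = 77 days.

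**Step 2. Does the survival call close the gap?**
- Content: footnote C lists survival and later therapy only, and the adverse event row is blank.
- Timing: 100 − 92 = 8 to 100 − 90 = 10 days before the window closes. Even with adverse event questions added, a call at 3 months would miss the last 8 to 10 days.

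**Step 3. Patients who complete 24 cycles**
- First 3-month visit: 90 − 7 = day 83 to 92 + 7 = day 99.
- Days left in the window: 100 − 99 = 1 to 100 − 83 = 17.
- Section 9.7 implies that adverse events are asked about at this visit. The last 1 to 17 days depend on recall at the 6-month visit.

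**Step 4. What one missed case would do**
- If the safety proportion is taken over all 40 patients, each patient whose only related serious event is missed lowers the observed proportion by 1/40 = 2.5 percentage points. The hierarchical model in 15.2.1 would shrink estimates, so this is the change in the raw proportion only.
- The documents give no rate of late or missed events, so no expected number of missed cases can be derived.

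**The case against.** Several passages narrow the gap.

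- **Known events do not lapse at day 30.** Serious events are followed to resolution or stabilization (9.8.2), as are drug-associated events (9.8). Section 9.8.3 requires follow-up of non-serious events that interrupt or stop the drug, or that are present at end of treatment. This stands, and it limits the gap to new-onset events.
- **Volunteered events must be recorded (9.8), and 6.4.1 expects serious events after day 30**, since it keeps concomitant medication records for them. This also stands, but it is passive capture, weaker than the continuous collection that 9.8.3 describes.
- **Medical history is ticked under survival follow-up.** A site might raise adverse events there. However, footnote C states the content of the call more narrowly, and the dedicated adverse event row is blank.
- **Section 9.7 requires questions at all study visits.** It helps completers. For patients who stop early, the contact is a telephone call with defined content, and no visit is scheduled between the safety visit and day 100.

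A reader might infer more than the documents support:

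- *That nobody on the trial is asked about adverse events after day 30.* Completers are seen every 3 months, and patients who enter second treatment are re-screened and return to scheduled review (7.6).
- *That late events are certainly under-counted.* No missed-event rate is given or derivable.
- *That drug half-lives measure the gap.* Residual drug is not a count of missed events, and the three antibodies differ.
- *That the toxicity pausing rule is undermined.* It counts events that warrant stopping treatment (15.3.2), so events arising after the last dose should affect it little.

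**Conclusion.** The inconsistency between sections 7 and 9 is real, applies to both regimens, and covers serious as well as non-serious events. For patients who stop early, 63 to 77 of the 100 days (nominally 70) have no scheduled active enquiry about new-onset adverse events. For completers the shortfall is small: up to 17 days, recoverable by recall at the 6-month visit. Ascertainment would therefore also differ between the two groups.

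Late related serious events may be under-counted in the secondary safety endpoint, and any error would be downward. Its size is unknown. The modelled endpoint changes only where a patient's first related serious event falls in the gap and goes unreported; missed non-serious events would affect the tabulations. The conclusion assumes that sites follow the calendars and footnotes as written. Because the remedy is nearly free, this should be corrected, although it does not threaten the primary objective.

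**What to change.** Reconcile sections 7.2, 7.3, 7.7, 9.7, 9.8.2 and 9.8.3:

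1. Tick "Review adverse events" at the first survival contact in both calendars.
2. Extend footnote C so that this contact also asks about new, ongoing and serious events since the day-30 visit.
3. Time this contact at or just after day 100. Alternatively, leave the 3-month call where it is and add a brief adverse event enquiry at day 100.
4. In 7.7, give completers an adverse event enquiry at or just after day 100 as well, and state in 9.7 that these telephone contacts count as occasions for adverse event questions.

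The cost is two calendar ticks, edits to the footnotes and to the short texts of 7.7 and 9.7, and a few questions per patient. Moving the first survival call delays it by about 10 days; the separate day-100 enquiry avoids that at the price of one more short contact. No treatment rule changes.

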10.0 REVIEW OF SAFETY INFORMATION: SPONSOR RESPONSIBILITIES

The sponsor must promptly review all information relevant to the safety of the drug obtained or otherwise received by the sponsor from foreign or domestic sources, including information derived from any clinical or epidemiological investigations, animal or in vitro studies, reports in the scientific literature, and unpublished scientific papers, as well as reports from foreign regulatory authorities and reports of foreign commercial marketing experience for drugs that are not marketed in the United States.

Note: The requirements of the Sponsor for the reporting of suspected adverse drug reactions to the FDA differ from the requirements of the Investigator (see below and [Investigator Responsibilities](#) on the O3IS website) for the reporting of adverse events to the Sponsor. Sponsor-investigators of IND applications are subject to compliance with both the adverse reaction reporting requirements of the Sponsor and the adverse event reporting requirements of the Investigator.

10.1 IND SAFETY REPORTS

The sponsor must notify FDA and all participating investigators (i.e., all investigators to whom the sponsor is providing drug under its INDs or under any investigator's IND) in an IND safety report of potential serious risks, from clinical trials or any other source, as soon as possible, but in no case later than 15 calendar days after the sponsor determines that the information qualifies for reporting under sections below. In each IND safety report, the sponsor must identify all IND safety reports previously submitted to FDA concerning a similar suspected adverse reaction,

and must analyze the significance of the suspected adverse reaction in light of previous, similar reports or any other relevant information..

10.2 SERIOUS AND UNEXPECTED ADVERSE EVENTS

The sponsor must report any suspected adverse reaction that is both serious and unexpected. The sponsor must report an adverse event as a suspected adverse reaction only if there is evidence to suggest a causal relationship between the drug and the adverse event, such as:

- A single occurrence of an event that is uncommon and known to be strongly associated with drug exposure (e.g., angioedema, hepatic injury, Stevens-Johnson Syndrome);
- One or more occurrences of an event that is not commonly associated with drug exposure, but is otherwise uncommon in the population exposed to the drug (e.g., tendon rupture);
- An aggregate analysis of specific events observed in a clinical trial (such as known consequences of the underlying disease or condition under investigation or other events that commonly occur in the study population independent of drug therapy) that indicates those events occur more frequently in the drug treatment group than in a concurrent or historical control group.

10.3 FINDINGS FROM OTHER STUDIES

The sponsor must report any findings from epidemiological studies, pooled analysis of multiple studies, or clinical studies whether or not conducted under an IND, and whether or not conducted by the sponsor, that suggest a significant risk in humans exposed to the drug. Ordinarily, such a finding would result in a safety-related change in the protocol, informed consent, investigator brochure (excluding routine updates of these documents), or other aspects of the overall conduct of the clinical investigation.

10.4 FINDINGS FROM ANIMAL OR IN VITRO TESTING

The sponsor must report any findings from animal or in vitro testing, whether or not conducted by the sponsor, that suggest a significant risk in humans exposed to the drug, such as reports of mutagenicity, teratogenicity, or carcinogenicity, or reports of significant organ toxicity at or near the expected human exposure. Ordinarily, any such findings would result in a safety-related change in the protocol, informed consent, investigator brochure (excluding routine updates of these documents), or other aspects of the overall conduct of the clinical investigation.

10.5 INCREASED RATE OF OCCURRENCE OF SERIOUS SUSPECTED ADVERSE REACTIONS

The sponsor must report any clinically important increase in the rate of a serious suspected adverse reaction over that listed in the protocol or investigator brochure.

10.6 SUBMISSION OF IND SAFETY REPORTS

The sponsor must submit each IND safety report in a narrative format or on Form FDA 3500A or in an electronic format that FDA can process, review, and archive. FDA will periodically issue guidance on how to provide the electronic submission (e.g., method of transmission, media, file formats, preparation and organization of files). The sponsor may submit foreign suspected adverse reactions on a Council for International Organizations of Medical Sciences (CIOMS) I Form instead of a Form FDA 3500A. Reports of overall findings or pooled analyses from published and unpublished in vitro, animal, epidemiological, or clinical studies must be submitted in a narrative format. Each notification to FDA must bear prominent identification of its contents, i.e., "IND Safety Report," and must be transmitted to the review division in the Center for Drug Evaluation and Research or in the Center for Biologics Evaluation and Research that has responsibility for review of the IND. Upon request from FDA, the sponsor must submit to FDA any additional data or information that the agency deems necessary, as soon as possible, but in no case later than 15 calendar days after receiving the request.

10.7 UNEXPECTED FATAL OR LIFE-THREATENING SUSPECTED ADVERSE REACTION REPORTS

The sponsor must also notify FDA of any unexpected fatal or life-threatening suspected adverse reaction as soon as possible but in no case later than 7 calendar days after the sponsor's initial receipt of the information.

